- after treatment of the first 10 subjects (5 in the TH arm and 5 in the control arm)
- at the conclusion of the study

In addition, the DSMB may convene additional meetings if necessary to ensure the ongoing monitoring and safety of the subjects treated with therapeutic hypothermia (TH). A copy of the DSMB charter is located in Appendix 2.

We will collect all treatment emergent and serious unsolicited adverse events during the index hospitalization. A treatment emergent adverse event is any untoward medical occurrence associated with the use of therapeutic hypothermia, whether or not considered related. The DSMB will be informed of expected adverse events, such as shivering, bleeding, and bradycardia, that result in termination of the protocol. Additionally, any unexpected adverse events while undergoing TH will be reported to the DSMB, whether deemed related to TH or not. All adverse event details will be provided to the DSMB prior to the meeting with ample time allowed for analysis. This will include details of the individual adverse events as well as the PI's analysis related to causality, severity and frequency. The DSMB will be responsible for

confirmation of the PI's assessment of all adverse events and final adjudication of all adverse events.

The DSMB will include the following individuals who have agreed to serve on it:

- [name] (University of Chicago Medicine – Section of Cardiology)
- [name] (Inova Health System – Section of Cardiology)
- [name] (University of Chicago Medicine – Section of Cardiology)

Payment to Subjects

Participants will not receive monetary compensation for their participation in this study. The cost of the TH catheters, thermal regulation system and associated monitoring will be part of the study costs and patients will not be charged for these services.

Informed Consent

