Appendix 2 – DSMB Charter

1. Introduction

This Charter is for the Data and Safety Monitoring Board (DSMB) for Cardiogenic Shock Intravascular Cooling Trial (CHILL-SHOCK). The DSMB will consist of a team of clinical researchers who are unaffiliated with this project. The members of the DSMB will not be investigators in this study and will be experienced in conducting and interpreting clinical trials. Their responsibilities will include reviewing the efficacy and safety endpoints at the set times points, as stated below. The Charter is intended to be a living document. The DSMB may wish to review it at regular intervals to determine whether any changes in the procedure are necessary.

2. Responsibilities of the DSMB

The DSMB is responsible for safeguarding the interests of study participants, assessing the safety and efficacy of study procedures, and for monitoring the overall conduct of the study.

The DSMB is an independent group advisory to the study PI and is required to provide recommendations about starting, continuing, and stopping the study. In addition, the DSMB is asked to make recommendations, as appropriate, to/about:

- Selection, recruitment, and retention of participants
- Adherence to protocol requirements
- Completeness, quality, and analysis of measurements
- Amendments to the study protocol and consent forms
- Confirmation of the PI's assessment of adverse events
- Final adjudication of all adverse events, as defined by *Table A* below
- Participant safety
- Notification of and referral for abnormal findings

3. DSMB Members

DSMB Chair: [name] University of Chicago Medicine Department of Medicine Section of Cardiology Assistant Professor of Medicine	[name], MSc Inova Health System Department of Medicine Section of Cardiology Professor of Medicine	[name] University of Chicago Medicine Department of Medicine Section of Cardiology Assistant Professor of Medicine
---------------------------------------------------------------------------------------------------------------------------------------------------------------------------	-----------------------------------------------------------------------------------------------------------------------------------------------	---------------------------------------------------------------------------------------------------------------------------------------------------

4. Scheduling, Timing, and Organization of Meetings: Data and Safety Monitoring Meetings

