The DSMB will meet (in person or via telephone conference) a minimum of 3 times:

- after treatment of the first 4 subjects (2 in the TH arm and 2 in the control arm)
- after treatment of the first 10 subjects (5 in the TH arm and 5 in the control arm)
- at the conclusion of the study

The DSMB may convene additional meetings if necessary to ensure the ongoing monitoring and safety of the subjects treated with TH.

A quorum of at least two (2) DSMB members needs to be present for a meeting to commence. Members may either be present in person or have the option to phone-in if unable to arrive at the meeting location.

All DSMB members will receive an agenda prior to the meeting. In the event that a DSMB member is unable to attend a meeting, that member will receive minutes, as well as any additional notes, with the opportunity to share any additional thoughts on the distributed information.

5. Grading and Attribution Methods for Adverse Events

Grading Scale

The DSMB and the study team will utilize the Adverse Event Grading Scale provided in Table A. All adverse events will be graded according to this scale, the PI will prepare data regarding adverse events for review by the DSMB prior to meeting, and any additional details will be provided to the DSMB by the PI, as necessary.

Table A – Safety Reporting Definitions

Term	Definition
Adverse Event (AE) Ref: ISO 14155-2011 Ref: MEDDEV 2.7/3 12/2010	
Any untoward medical occurrence, unintended disease or injury, or any untoward clinical signs (including an abnormal laboratory finding) in subjects, users or other persons, whether or not related to the investigational medical device.
 
This definition includes events related to the procedures involved (any procedure in the clinical investigation plan).

Adverse Device Effect (ADE) Ref: ISO 14155-2011 Ref: MEDDEV 2.7/3 12/2010	
Adverse event related to the use of an investigational medical device
 
NOTE 1: This definition includes any adverse event resulting from insufficient or inadequate instructions for use, the deployment, the implantation, the installation, the operation, or any malfunction of the investigational medical device.
 
NOTE 2: This definition includes any event resulting from use error or from intentional misuse of the investigational medical device.

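### Two of the three DSMB members, including the Chair, come from the enrolling hospital's cardiology section, and the quorum rule lets them adjudicate adverse events without the only outside member

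*Combined protocol and SAP*

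**What the plan says.** - **Independence.** Section 1 of the Charter says: "The DSMB will consist of a team of clinical researchers who are unaffiliated with this project". It adds: "The members of the DSMB will not be investigators in this study". Section 2 says: "The DSMB is an independent group advisory to the study PI".
- **Membership.** Section 3 lists three people. The Chair and one other are each described as "University of Chicago Medicine Department of Medicine Section of Cardiology Assistant Professor of Medicine". The third is at "Inova Health System Department of Medicine Section of Cardiology Professor of Medicine". The list in the protocol body (D. Data Safety Monitoring Board) agrees: two of its three entries read "University of Chicago Medicine – Section of Cardiology".
- **Quorum.** Section 4 says: "A quorum of at least two (2) DSMB members needs to be present for a meeting to commence". It sets no condition on which two. An absent member is sent the minutes and may comment.
- **Task.** The protocol body gives the board confirmation of the PI's assessments and "final adjudication of all adverse events". Section 2 of the Charter repeats this and adds recommendations on continuing or stopping the study.
- **Setting.** Under Methods, A. Patient Population, every patient is admitted to the University of Chicago CCU and assignment is not blinded.

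**The concern.** A monitoring board protects patients and the credibility of the results because its judgement is separate from that of the people running the trial. Here the charter asserts independence, but its membership and quorum rules allow a valid meeting made up only of cardiologists from the hospital where every patient is treated.

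The stakes are higher than in a trial with a blinded efficacy endpoint. The stated objective is safety and all four primary endpoints are safety events. The board works from the PI's own view of causality, severity and frequency. The documents give no numerical stopping threshold, so the decision to halt rests on judgement. If that judgement leans towards the investigators' reading, both the attribution of events and the advice to continue are affected.

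**Working it through.** The plan gives no figure to reproduce. The check is a count of permitted meetings, then a comparison of the board's remit with the endpoints.

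**1. Who can meet**

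Inputs: three members, of whom A (Chair) and B are from the University of Chicago Section of Cardiology and C is from outside (Charter section 3); minimum attendance two (Charter section 4).

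Permitted attendance sets = C(3,2) + C(3,3) = 3 + 1 = 4:

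| Present | Outside member there? | In-house share |
|---|---|---|
| A, B | No | 2/2 |
| A, C | Yes | 1/2 |
| B, C | Yes | 1/2 |
| A, B, C | Yes | 2/3 |

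One of the four sets excludes the outside member and still meets the quorum. This counts what the rule permits. It is not a probability that such a meeting will occur.

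**2. What an in-house meeting could settle**

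The Charter attaches no higher quorum to any decision, so the A, B meeting has the board's full remit, including final adjudication and the continue or stop recommendation. The outside member's comment comes after the meeting. The Charter does not say that it carries a vote or holds a decision open.

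**3. Whether adjudication reaches the primary endpoints**

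Table A of the Charter defines an adverse event broadly and includes abnormal laboratory findings. The overlap with the list under Endpoints is:

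- *Hypokalemia.* The primary endpoint is potassium below 3.0 mEq/L without another identifiable cause. The section on mitigating TH risks makes the same finding an adverse event in cooled patients. Excluding other causes is a causal judgement.
- *Arrhythmia.* The primary endpoint includes treatment with a temporary pacemaker. The risk section counts bradycardia needing temporary pacing as an adverse event of cooling only if there was no prior conduction disease. For ventricular arrhythmia it calls for a judgement on whether hypothermia was the cause.
- *Bleeding.* The primary endpoint requires attribution to catheter insertion or to resulting coagulopathy. The risk section classifies bleeding adverse events and again refers to attribution to TH.

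So three of the four primary endpoints overlap events that the board adjudicates and that involve a causal judgement in the endpoint or in the matching adverse event rule.

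**4. What one classification is worth**

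Planned size is 10 per arm (Target Enrollment and Study Duration). Moving one patient across the event line changes that arm's rate by 1/10 = 10 percentage points. Simple randomization may not give exactly 10 and 10; at 8 or 12 in an arm the step would be 1/8 = 12.5 or 1/12 = 8.3 points.

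**5. Recusal**

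Under Procedures, the PI is kept out of patients' clinical management. The text supplied has no matching sentence for DSMB members, so a member who had treated an enrolled patient would not be barred from adjudicating that patient's events.

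**The case against.** The best defence is that the charter does what it says. It claims separation from the project, not from the hospital, and it excludes investigators from membership. A reader might infer that the membership list contradicts the independence statement. It does not, and the affiliations are disclosed in both places. That part of the defence stands.

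Other tempting inferences also go further than the documents:

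- *The members are direct colleagues of the investigators.* The investigators' sections are not given in the text supplied, so this is plausible but not established. Nor does anything show that a DSMB member works in the CCU.
- *The board formally adjudicates the primary endpoints.* No section assigns that task. The board adjudicates adverse events as defined in Table A, and the link is the overlap shown above.
- *In-house members outvote the outside member.* The charter has no voting rule, and any single member of a three-person board is in a minority. The case rests on presence at the meeting, not on votes.
- *The Chair should be replaced.* That is a preference; the weakness can be managed without it.

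There are real mitigations. Members may attend by telephone, all receive the agenda, and an absent member may comment. Serious events go to FDA within 48 hours of PI knowledge, and unanticipated device effects go to FDA and the IRB, without waiting for the board (Charter, Table C). These lower the risk that an event goes unreported. They do not bring an outside view into the adjudication before it is final.

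A further fair objection is that making one named person mandatory could block an urgent safety meeting. The fix has to allow for that.

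**Conclusion.** The point holds as a weakness in the board's structure. Two of three members, including the Chair, share the enrolling hospital's cardiology section, and one of the four permitted attendance sets gives final adjudication and a continue or stop recommendation with no outside member present. The consequence is potentially material because the trial is open-label and single-centre, the PI supplies the causality analysis, and one reclassified event is worth about 10 percentage points in an arm.

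The conclusion assumes that the quorum sentence means any two members, and that no separate conflict-of-interest or recusal rule exists outside the text supplied. If one does, the recusal part falls away and the quorum part remains. No actual bias is shown or alleged. For a 20-patient pilot this should be corrected, but it is not a reason to withhold the trial.

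**What to change.** In Charter section 4, replace the quorum sentence with:

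> *A quorum is two members and must include the member from outside the University of Chicago. An urgent safety meeting may proceed with any two members, but adjudications and a recommendation to continue are not final until the outside member has reviewed them.*

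And add:

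> *A member who had a clinical role in an enrolled patient's care does not take part in adjudicating that patient's events.*

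For ordinary meetings this removes the A, B set and leaves three, all with the outside member present. It does not change the in-house share in those three. Its purpose is to ensure that an outside view is heard before a decision is final. An urgent recommendation to pause or stop is not delayed.

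The cost is a few sentences in a document that the charter itself expects to be revised. No new members, analyses or clinical procedures are needed. The downside is that meetings, of which at least three are planned and which may be held by telephone, must be scheduled around one person. Where recusal removes an in-house member from a case, the other two still form a quorum. If the outside member is the one recused, the charter should allow the remaining two to adjudicate that case and record why.

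The fix leaves one related matter untouched. The Charter's section on reports of deliberations lets the study team go on asking for information until it agrees with a recommendation. That also bears on independence and is worth considering at the same revision.

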 - c. Vascular injury

Mitigating Risks associated with TH:

Shivering is the most common risk associated with TH. Shivering is a normal physiological response to cooling as it allows the body to expend energy and generate heat. This leads to increasing metabolic demands and subsequent oxygen consumption. Various strategies can be used to combat shivering and have these have been well described in the literature. In patients that are intubated, the most common means of combating shivering is a combination of benzodiazepines, opioid analgesics, and/or neuromuscular blockade.¹⁶ In awake patients, combination of meperidine and warming of skin with air-warming products such a 'Bair Hugger

blanket' (3M, St. Paul, MN) hugger' are utilized.¹⁷ Meperidine is the most beneficial agent to prevent shivering and previous studies have demonstrated significant lowering of the shivering threshold with meperidine.^{17,18} Given that intravascular cooling therapy is common in multiple ICU settings, including the cardiac care unit (CCU), protocols are already in place for the management of shivering, with an institutional-approved anti-shivering protocol often used in patients undergoing TH.¹⁸ In the event of persistent shivering despite therapy with intravenous sedatives, anesthetics (i.e. propofol or meperidine) and/or paralytic agents in intubated patients, the TH protocol will be stopped and patients will be rewarmed to normothermia.

Therapeutic hypothermia may potentially increase the risk of arrhythmias and will be evaluated in this trial. Bradycardia is expected with TH. In the previously published studies, the reduction in heart rate is not significant enough to cause hemodynamic compromise.^{9,17,19} However, if a patient is noted to be persistently bradycardic, with signs or symptoms requiring temporary pacemaker insertion, the TH protocol will be stopped. Bradycardia requiring temporary pacing will be considered an adverse event of cooling if the patient did not have underlying conduction system disease (i.e. first or second degree AV block) prior to cooling. In such cases, patients will be rewarming to normothermia per the rewarming protocol currently in place for intravascular cooling of critically ill patients.

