Appendix 1 – Schedule of Study Activities

	Baseline	18-24 hours (after randomization)	48-96 hours (after randomization)	30-day Follow-Up	90-day Follow-Up
Informed Consent	X				
Review Medial History	X				
Review Medication History	X				
Height and Weight	X				
Vital Signs ^a	X	X	X		
Echocardiogram (TTE)	X	X	X		
Electrocardiogram (ECG)	X	X	X		
Hemodynamics ^b	X	X	X		
Blood Tests ^c	X	X	X		
Vasoactive Medication Dosing		X			
Potassium (pts randomized to cooling)		Q 4 hours			
Glucose Checks (pts randomized to cooling)		Q 1 hour			
Urine Output	X	X	X		
Randomization	X				
Adverse Events		X	X	X ^d	X ^d

^a blood pressure, heart rate, temperature (bladder or esophageal), respiratory rate

^b RA pressures, RV pressures, PA pressures, pulmonary capillary wedge pressure (PCWP), Fick cardiac output and cardiac index, systemic vascular resistance (SVR), pulmonary vascular resistance (PVR), cardiac power and cardiac power index, mixed venous saturation (MVO2)

^c serum lactate level, basic metabolic panel, hepatic function, coagulation parameters, complete blood count (CBC), arterial blood gas (ABG), and optional blood samples for future research

^d to be completed in clinic, when possible, or by phone

^e items to be charged to research during cooling include: meperidine

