Serious Adverse Event (SAE) Ref: ISO 14155-2011 Ref: MEDDEV 2.7/3 12/2010	
Adverse event that:
 
• Led to death,• Led to serious deterioration in the health of the subject, that either resulted in:
○ a life-threatening illness or injury, or○ a permanent impairment of a body structure or a body function, or

Table A – Safety Reporting Definitions

Term	Definition
	
○ in-patient or prolonged hospitalization of existing hospitalization, or○ medical or surgical intervention to prevent life-threatening illness or injury or permanent impairment to a body structure or a body function● Led to fetal distress, fetal death, or a congenital abnormality or birth defect. 
NOTE: Planned hospitalization for a pre-existing condition, or a procedure required by the clinical investigational plan, without serious deterioration in health, is not considered a serious adverse event.

Serious Adverse Device Effect (SADE) Ref: ISO 14155-2011 Ref: MEDDEV 2.7/3 12/2010	Adverse device effect that has resulted in any of the consequences characteristic of a serious adverse event.
Unanticipated Adverse Device Effect (UADE) Ref: 21 CFR Part 812	Any serious adverse effect on health or safety or any life-threatening problem or death caused by, or associated with, a device, if that effect, problem, or death was not previously identified in nature, severity, or degree of incidence in the investigational plan or application (including a supplementary plan or application), or any other unanticipated serious problem associated with a device that relates to the rights, safety, or welfare of subjects.
Device Deficiency Ref: ISO 14155-2011 Ref: MEDDEV 2.7/3 12/2010	
A device deficiency is any inadequacy of a medical device with respect to its identity, quality, durability, reliability, safety or performance.
 
NOTE: Device deficiencies include malfunctions, misuse or use errors, and inadequate labeling.

Abbreviations: EC=Ethics Committee; IRB=Institutional Review Board

Underlying diseases are not reported as AEs unless there is an increase in severity or frequency during the course of the investigation.

Relationship to Study Device(s) and Reporting Requirements

The Investigator will assess the relationship of the AE to the study device as related or unrelated.

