Table B – Criteria for Assessing Relationship of Study Device to Adverse Event

Classification	Description
Unrelated	The adverse event is determined to be due to a concurrent illness or effect of another device/drug and is not related to the investigational product.
Related	
• The adverse event is determined to be potentially related to the investigational product, and an alternative etiology is equally or less likely compared to the potential relationship to investigational product, or• There is a strong relationship to investigational product, or recurs on re-challenge, and another etiology is unlikely, or• There is no other reasonable medical explanation for the event.

Table C – Adverse Event Reporting

Event Classification	Event Recording	Communication to FDA	Communication to IRB
Adverse Event	
• Event reviewed and classified by PI• Event recorded in Oncore Adverse event database	Detail of all AE's will be given at time of annual report.	Details provided at time of annual review, per IRB policy.
Serious Adverse Event including Serious Adverse Device Effects	
• Event reviewed and classified by PI• Event recorded in Oncore Adverse event database	Reported via From 3500 within 48 hours of PI knowledge.	Details provided at time of annual review, per IRB policy (as these are not unanticipated events).
Unanticipated Adverse Device Effect / Unanticipated Serious Adverse Device Effect	
• Event reviewed and classified by PIStudy will be halted if event presents a significant or unreasonable risk to subjects enrolled in the study• Event recorded	Reported as soon as possible, but within 48 hours of PI knowledge, via From 3500.	UADE reported within 10 days of PI knowledge USADE reported directly to IRB Chairman upon PI knowledge, followed by formal reporting to the IRB within 48 hours. Study will be halted if event presents a

Table C – Adverse Event Reporting

Event Classification	Event Recording	Communication to FDA	Communication to IRB
	in Oncore Adverse event database		significant or unreasonable risk to subjects enrolled in the study

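### Table B judges relatedness to the device alone, so harm from drugs given to permit cooling can be filed as Unrelated, affecting the related-event count and, for serious unanticipated events, IRB reporting and the halt rule

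*Combined protocol and SAP*

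**What the plan says.** The charter's section on relationship to the study device sets a two-way choice: "The Investigator will assess the relationship of the AE to the study device as related or unrelated". Table B supplies the criteria. An event is Unrelated if it is "due to a concurrent illness or effect of another device/drug and is not related to the investigational product". The first route to Related requires that "an alternative etiology is equally or less likely compared to the potential relationship to investigational product". The other two routes require that another cause is unlikely, or that there is no other reasonable medical explanation. The term investigational product is not defined. Table A defines an adverse device effect as "Adverse event related to the use of an investigational medical device".

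The protocol's section on mitigating TH risks describes the treatment of shivering. For intubated patients, "the most common means of combating shivering is a combination of benzodiazepines, opioid analgesics, and/or neuromuscular blockade". For the others: "In awake patients, combination of meperidine and warming of skin with air-warming products". TH is stopped only if shivering persists despite drug treatment. A footnote to Appendix 1 reads "items to be charged to research during cooling include: meperidine".

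The Objective section presents the trial as a pilot of the safety and tolerability of TH in cardiogenic shock.

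**The concern.** The trial tests a strategy: catheter, cooling, rewarming, and the drugs that make cooling tolerable. The attribution rule tests something narrower. If a patient has respiratory depression or hypotension after an anti-shivering drug, the drug is the nearer cause and the device is not. Read literally, the rule allows that event to be set aside as the effect of another drug, although cooling is the reason the drug was given.

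Two things are at stake. A reader who takes the related-event count as the harm of TH would see too low a figure. And a serious event that nobody anticipated could take a slower reporting route, because only the row of Table C for unanticipated device effects carries expedited IRB reporting and an explicit halt rule. The primary safety endpoints do not cover respiratory depression, new intubation or sedation-related hypotension, so adverse-event reporting is the main channel for these harms.

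**Working it through.** The plan gives no figure on this point, so there is none to reproduce. The check sets the texts side by side and then sizes the consequence.

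**1. Apply Table B to a test case.** An awake TH patient receives meperidine for shivering and then has respiratory depression.

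- *If investigational product means the device:* the drug is the more likely cause, so the first route to Related fails. Another etiology is likely and a reasonable alternative explanation exists, so the other two fail as well. Both parts of Unrelated are met.
- *If it means the TH strategy:* the drug is part of the product, so the second part of Unrelated fails and the event is Related.

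The result turns on an undefined term. The sentence above Table B names the study device, which favours the narrow reading without compelling it.

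**2. Follow each label through Table C.**

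| Event | Filed Related | Filed Unrelated | What changes |
|---|---|---|---|
| Non-serious | FDA annual report; IRB annual review | Same (no separate row for non-serious device effects) | Nothing |
| Serious, anticipated | FDA within 48 hours; IRB annual review | Same row | Nothing |
| Serious, unanticipated | FDA within 48 hours; IRB within 10 days, or the IRB Chairman at once with a formal report within 48 hours; halt rule | FDA within 48 hours; IRB annual review; no halt rule in that row | IRB timing and halt rule |

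Enrolment is expected to finish within 6 months, so an annual IRB review could come after the last patient is treated.

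**3. Size.** The TH arm has 10 patients, so each refiled patient moves the related proportion by 1/10 = 10 percentage points. The documents give no rate for this harm, so a range is assumed. The chance of at least one such event is 1 − (1 − p)^10:

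- p = 5%: 1 − 0.95^10 = 40%
- p = 10%: 1 − 0.90^10 = 65%
- p = 20%: 1 − 0.80^10 = 89%
- p = 30%: 1 − 0.70^10 = 97%

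Suppose 2 of 10 TH patients have such harm. The all-cause count is 2/10, with an exact (Clopper-Pearson) 95% interval of 2.5% to 55.6%. If both are filed Unrelated and no other event is related, the related count is 0/10, with an upper limit of 1 − 0.025^(1/10) = 30.8%. The all-cause count stays at 2/10.

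**4. Exposure data.** Item 7 of Data Collected and the dosing row of Appendix 1 cover vasoactive drugs only. Item 1 lists medications in general terms, but Appendix 1 schedules medication history at baseline only. Sedatives, opioids and paralytics may themselves affect the hemodynamic and vasopressor endpoints.

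**The case against.** The strongest reply is that Table B does not file anything by itself. Unrelated has two parts, no anti-shivering drug is named, and an investigator could reasonably call harm from meperidine given for cooling Related. That stands: the rule permits the misfiling and does not require it.

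A reader might infer several stronger things that the documents do not support.

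- *Harms of TH are undercounted overall.* They are not. The Data Safety Monitoring Board section collects treatment-emergent events whether or not they are considered related and sends unexpected events during TH to the DSMB on the same basis. Table A also counts events from any procedure in the plan as adverse events. It sets scope and Table B sets attribution, so the two do not conflict.
- *Such events escape device-effect reporting.* Only the unanticipated row differs. Even there, Table A's definition reaches events associated with a device, which is wider than Table B's Related, and the DSMB can call extra meetings and recommend stopping whatever the label.
- *Only TH patients can receive these drugs.* The documents do not say that sedatives, opioids or paralytics are reserved for cooling or withheld from controls. The link is clearest for meperidine.
- *The earlier 14-patient series measures the harm.* In it, 5 of 14 patients breathed spontaneously. Scaled to 10 patients this is 5/14 × 10 = 3.6, but that counts possibly unintubated patients. It is neither a harm rate nor proof of meperidine exposure.

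It is also fair to say that Statistical Methods plans no analysis of a related-event rate, that the risk and data lists are stated to be non-exhaustive, and that the DSMB makes the final adjudication. The last point helps only in part, because the DSMB works under the charter that contains Table B.

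**Conclusion.** The point holds in a limited form. Relatedness is judged to the device, and the text allows harm from drugs given to permit cooling to be called Unrelated. The effect is confined to the count of intervention-related events and, for a serious unanticipated event filed that way, to expedited IRB reporting and the halt rule attached to that row of Table C. Total adverse events, DSMB visibility and the 48-hour FDA report are unaffected.

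This rests on two assumptions: that an investigator takes the narrow reading of investigational product, and that the Table B label decides the row of Table C. The charter states neither. The event rates above are illustrative. Severity is minor to moderate. The case for acting is that the objective is the safety and tolerability of TH, the arm is small, and the repair is cheap.

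**What to change.** 1. Reword the sentence above Table B, and Table B itself, so that relatedness is judged to the study intervention: the device, catheter insertion, cooling, rewarming, and drugs given specifically to permit cooling. Limit the other-device-or-drug clause to treatments outside that list.
2. Leave the Table A definitions as they are, since they cite an ISO standard and a federal regulation. Add one sentence to Table C saying that a serious unanticipated event related to any of these components follows the row for unanticipated device effects.
3. Record sedative, opioid and paralytic exposure, with the reason given, and any new intubation during the intervention period in both arms. Rewording Table B will not separate drug effects from temperature effects, but these fields allow exposure to be described beside the hemodynamic and vasopressor results.
4. Report adverse events of any cause by arm beside the related count.

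Sedation effects could also be added to the anticipated risks, for completeness. That should not be offered as a remedy for lost expedited reporting. An event already identified in the plan in nature, severity and incidence would generally no longer count as unanticipated, so listing it narrows that route.

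The cost is charter wording, a few case-report fields, and a related-event count that may look slightly less favourable to TH. The sample size, endpoints and clinical rules do not change.
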